# 1. DEFINITIONS AND/OR ABBREVIATIONS

ADR	Adverse drug reaction
AE	Adverse event
ALP	Alkaline phosphatase
ALT	Alanine aminotransferase
AST	Aspartate aminotransferase
ATC	Anatomical Therapeutic Chemical
ATP	Adenosine triphosphate
AUC	Area under the concentration-time curve
BAT	Brown-like adipose tissue
BMI	Body Mass Index
BUN	Blood urea nitrogen
°C	Degrees Celsius
CBC	Complete blood count
CDC	Center for Disease Control
cGMP	Current Good Manufacturing Practices
CI	Confidence Interval
CK-MM	Creatine Kinase - Muscle
C max	Maximum observed concentration
CNS	Clinically not significant
CRF	Case Report Form
CPK	Creatine phosphokinase
CRP	C-reactive protein

Medi-Stat Statistics in Medicine	DOCUMENT NUMBER: 050-BST-PLN-001	PAGE: 6 of 31
TITLE: Statistical Analysis Plan		EFFECTIVE DATE: 14/Nov/2018 REVISION NUMBER: 2.0

CS	Clinically significant
СТС	Common terminology criteria
CTCAE	Common Terminology Criteria for Adverse Events
DICOM	Digital Imaging and Communications in Medicine
DSMB	Data and Safety Monitoring Board
EC	Ethics Committee
ECG	Electrocardiogram
EF	Efficacy analysis set
ER	Emergency room
FDA	Food and Drug Administration
FFA	Free fatty acids
FIFO	First In First Out
FLASH	Fast-low-angle shot
FOB	Functional Observational Battery
GLP	Good Laboratory Practice
GTTP	Gamma-glutamyltransferase
HBV	Hepatitis B virus
HCRC	Hadassah Clinical Research Center
HCV	Hepatitis C virus
H&E	Hematoxylin and eosin stain
HDL	High-density lipoprotein
HED	Human equivalent dose
HIV	Human immunodeficiency virus
IC 50	Half maximal inhibitory concentration

ICF	Informed Consent Form	
ICH-GCP	International Conference on Harmonization Good Clinical Practice	
IFN	Interferon	
IL	Interleukin	
INR	International normalized ratio	
IRB	Institutional Review Board	
LDL	Low-density lipoprotein	
LDH	Lactate dehydrogenase	
LPL	Lipoprotein lipase	
MCH	Mean corpuscular hemoglobin	
MCHC	Mean corpuscular hemoglobin concentration	
MCP	Monocyte chemoattractant protein	
MCV	Mean corpuscular volume	
MD	Medical Doctor	
MEDDRA	Medical Dictionary for Regulatory Activities	
MPV	Mean platelet volume	
MRI	Magnetic Resonance Imaging	
NHANES	National Health and Nutrition Examination Survey	
NOAEL	No observed adverse effect level	
NSAIDs	Non Steroid Anti-Inflammatory Drugs	
PI	Principal Investigator	
PK	Pharmacokinetics	
PKA	PK Analysis set	
PT	Prothrombin time	
PK PKA	Pharmacokinetics  PK Analysis set	

Medi-Stat Statistics in Medicine	DOCUMENT NUMBER: 050-BST-PLN-001	PAGE: 8 of 31
TITLE: Statistical Analysis Plan		EFFECTIVE DATE: 14/Nov/2018 REVISION NUMBER: 2.0

PTT	Partial thromboplastin time	
QA	Quality Assurance	
RBC	Red blood cells	
RDW	Red cell distribution width	
SA	Safety analysis set	
SAE	Serious adverse event	
SAP	Statistical Analysis Plan	
SAS	Statistical Analysis Software	
SAT	Subcutaneous adipose tissue	
SC	Subcutaneous	
SFM	Subcutaneous fat mass	
SUSAR	Suspected Unexpected Serious Adverse Reaction	
T 1/2	Terminal half-life	
TAG	Triacylglycerols	
TBD	To be determined	
TC	Total Cholesterol	
TG	Triglycerides	
TGF	Transforming growth factor	
T max	Time of maximum observed sample concentration	
TNF	Tumor necrosis factor	
UCP1	Uncoupling protein 1	
ULN	Upper limit of normal	
US/USA	United States/United States of America	

Medi Stat Statistics in Medicine	DOCUMENT NUMBER: 050-BST-PLN-001	PAGE: 9 of 31
TITLE: Statistical Analysis Plan		EFFECTIVE DATE: 14/Nov/2018 REVISION NUMBER: 2.0

WAT	White adipose tissue
WBC	White blood cells
WHO	World health organization
WHR	Waist to hip ratio

Medi Stat Statistics in Medicine	DOCUMENT NUMBER: 050-BST-PLN-001	PAGE: 10 of 31
TITLE: Statistical Analysis Plan		EFFECTIVE DATE: 14/Nov/2018 REVISION NUMBER: 2.0

## 2. PURPOSE

- 2.1 The purpose of this document is to describe in detail the Statistical Analysis Plan of clinical study procedures carried out by Medistat Ltd.
- 2.2 This document serves Medistat Ltd. as a guiding document for all statistical analyses performed at the end of each clinical study.
- 2.3 This SAP is specific to Raziel Therapeutics LTD, study RZL-012-P2aUS-001.4
- 2.4 This SAP aims to provide details on: sample size calculation, efficacy analyses and safety analyses.

## 3. SCOPE

- 3.1 This document applies to all members of the statistical & data management units in Medistat Ltd.
- 3.2 This document includes the main and interim study trial analysis.

Medi Stat Statistics in Medicine	DOCUMENT NUMBER: 050-BST-PLN-001	PAGE: 11 of 31
TITLE: Statistical Analysis Plan		EFFECTIVE DATE: 14/Nov/2018 REVISION NUMBER: 2.0

# 4.2 Raziel's Responsibilities

- 4.2.1 To review and approve the SAP and related documents prior to database lock.
- 4.2.2 To review and approve the draft and final statistical report and listing appendix.

Medi Stat Statistics in Medicine	DOCUMENT NUMBER: 050-BST-PLN-001	PAGE: 12 of 31
TITLE: Statistical Analysis Plan		EFFECTIVE DATE: 14/Nov/2018 REVISION NUMBER: 2.0

#### 5. PROCEDURE

#### 5.1 Introduction

[figure not shown]
- 5.1.1 This Statistical Analysis Plan (SAP) is based on the study protocol final version V1.4, dated 4 March, 2018.
- 5.1.2 This Statistical Analysis Plan (SAP) contains details of the statistical analyses that will be performed, providing a more detailed description of the approach defined in the study protocol. Definitions of variables and populations used for the analyses are also included. The SAP will be finalized and signed prior to hard lock of the database.
- 5.1.3 General output specifications are provided; examples are given of calculations of derived variables.

#### 5.2 Rationale

- 5.2.1 The purpose of this study is to test safety and efficacy of a new chemical entity, RZL-012, in converting WAT into a thermogenic tissue and reducing fat-mass in overweight and obese males
- 5.2.2 RZL-012 investigational drug is intended for a single dose in multiple injections into the subcutaneous fat. The injection dosing regimen and technique is crucial for the therapy safety and efficacy. The RZL-012 drug is a ready to use liquid to be injected to the subcutaneous fat, supplied in a 1 vial kit. 1 vial contains 250 mg/4.8 mL RZL-012 in formulation F12. The vehicle is a ready to use liquid to be injected to the subcutaneous fat, supplied in a 1 vial kit. 1 vial contains 4.8 mL of formulation F12.

## 5.3 Study Objectives and Endpoints

- 5.3.1 Primary Objectives:
- 5.3.2 Evaluation of the overall safety and preliminary efficacy of RZL-012 after injection into the subcutaneous fat.
- 5.3.3 Primary Endpoints

- 5.3.4 Safety: The main objective is the evaluation of the overall safety of RZL-012 injection into the subcutaneous fat. Therefore, the primary endpoint will be the incidence of intolerable side effects and all adverse events of RZL-012 injection into the subcutaneous fat. The dose escalation scheme will be stopped if at any dose cohort, 2 patients will experience intolerable side effects.
- 5.3.5 Efficacy: The primary endpoint for efficacy is a significant thermogenesis at the injected site compared with the contra-lateral, non-injected site. This was monitored by sensitive (± 0.1 °C) Infra-Red thermal camera. A thermogenic effect is defined by an increase of 1 °C in the injected site when compared to the surroundings and/or the non-injected site, apparent at least 28 days after injection and non-related to inflammatory response as determined by inflammatory cytokines. The primary efficacy evaluation will be supported by results from secondary endpoints, including MRI, biopsy and biomarkers
- 5.3.6 Secondary Objectives:
- 5.3.7 Determination of RZL-012 pharmacodynamics and pharmacokinetics. Evaluation of the existence of a thermogenic effect and the extent, duration and tissue associated changes of the thermogenic response to RZL-012, via minimal invasive means (injected-site thermogenesis imaging, Magnetic Resonance Imaging (MRI) and biopsy) after subcutaneous injection into fatty tissue below the skin.
- 5.3.8 Secondary Endpoints
- 5.3.9 Duration of the thermogenic effect, defined as a net-delta  $\geq 1$
- 5.3.10 Local reduction in fat mass as determined by MRI.
- 5.3.11 Clinical laboratory changes from baseline including improvement in fasting blood glucose and lipid profile.
- 5.3.12 Establishing pharmacokinetic profile for RZL-012.
- 5.3.13 Anthropometric changes from baseline, including body weight change.
- 5.3.14 Elucidation of the histological changes account for the thermogenic effect by biopsy of the injection site.
- 5.3.15 Change from baseline in inflammatory markers and cytokines.
- 5.4 Overall study design and plan

Medi Stat Statistics in Medicine	DOCUMENT NUMBER: 050-BST-PLN-001	PAGE: 14 of 31
TITLE: Statistical Analysis Plan		EFFECTIVE DATE: 14/Nov/2018 REVISION NUMBER: 2.0

- 5.4.1 Study Design
- 5.4.2 This is a consecutive 4 cohort, dose escalation placebo-controlled clinical trial in overweight and obese subjects. All cohorts will be comprised of 6 active (RZL-012) and 2 placebo subjects.
- 5.4.3 Within each cohort, dosing of the first 3 subjects will progress consecutively from one individual to the other at 7-day intervals. For additional precaution, the first 3 subjects will be forced randomized into 2 active and 1 control. This study design will allow the physicians to monitor safety in a two subjects at each dose, nevertheless the blindness will remain intact. The remaining subjects in a cohort will be randomized to either active treatment or placebo in a ratio determined by the number of subjects targeted for each cohort. Dosing of the next subjects will be in couples and the last subjects will be in a triplet.

## 5.4.4 Schedule of Assessments

[figure not shown]
Study Procedure	Screening Day 1	Screeni ng Day 2	Clinic Admissi on	Baseline (Treatme nt)	Visit Schedule (Days 1 to 28)					Follow- up Schedu le for the highest dose cohorts (Days 29 - 168)	
Study Day a	Day a -(- 28) throug h Day (-7)	Day a -(- 14) through Day (-2)	Day (-1)	Day a 0	Da y 1	Da y 3	Da y 7	Day 14	Da y 21	Da y 28	Day 56, 84, 112, 140, 168
Signed informed consent	X										
Medical history	X		X								

Medi Stat Statistics in Medicine	DOCUMENT NUMBER: 050-BST-PLN-001	PAGE: 15 of 31
TITLE: Statistical Analysis Plan		EFFECTIVE DATE: 14/Nov/2018 REVISION NUMBER: 2.0

Study Procedure	Screening Day 1	Screeni ng Day 2	Clinic Admissi on	Baseline (Treatme nt)	Vi	Visit Schedule (Days 1 to 28)					Follow- up Schedu le for the highest dose cohorts 1 (Days 29 - 168)
Study Day a	Day a -(- 28) throug h Day (-7)	Day a -(- 14) through Day (-2)	Day (-1)	Day a 0	Da y 1	Da y 3	Da y 7	Day 14	Da y 21	Da y 28	Day 56, 84, 112, 140, 168
Complete physical exam	X									X	
Serology assays (HBV, HCV, HIV)	X										
Fasting glucose	X		X								
Fasting glucose, insulin, leptin and lipid profile (including FFA)			X							X	Every 28 days
Inflammatory markers and Cytokines - In subject of the 2 nd , 3 rd and 4 th cohorts b			X				X	X	X	X	

Medi Stat Statistics in Medicine	DOCUMENT NUMBER: 050-BST-PLN-001	PAGE: 16 of 31
TITLE: Statistical Analysis Plan		EFFECTIVE DATE: 14/Nov/2018 REVISION NUMBER: 2.0

Study Procedure	Screening Day 1	Screeni ng Day 2	Clinic Admissi on	Baseline (Treatme nt)	Visit Schedule (Days 1 to 28)					Follow- up Schedu le for the highest dose cohorts (Days 29 - 168)	
Study Day a	Day a -(- 28) throug h Day (-7)	Day a -(- 14) through Day (-2)	Day (-1)	Day a 0	Da y 1	Da y 3	Da y 7	Day 14	Da y 21	Da y 28	Day 56, 84, 112, 140, 168
Photography of site of injection and contralateral	X				X		X	X	X	X	Every 28 days
MRI section around the umbilicus		X								X	
MRI section around the umbilicus – for cohort 2											On Day

Study Procedure	Screening Day 1	Screeni ng Day 2	Clinic Admissi on	Baseline (Treatme nt)	Vi	isit Scl	nedule	(Days	s 1 to 2	:8)	Follow- up Schedu le for the highest dose cohorts 1 (Days 29 - 168)
Study Day a	Day a -(- 28) throug h Day (-7)	Day a -(- 14) through Day (-2)	Day (-1)	Day a 0	Da y 1	Da y 3	Da y 7	Day 14	Da y 21	Da y 28	Day 56, 84, 112, 140, 168
MRI section around the umbilicus – for 3 rd and 4 th cohort or in cohort 2 if 2 subject experience intolerable side effects in cohort 3)											Every 28 days
Anthropometri c measurements: (weight, height) BMI, (waist & hip circumference) WHR	X	X	X							X	Every 28 days
Weight – by the subjects at home –							X	X	X		On weeks when

Medi Stat Statistics in Medicine	DOCUMENT NUMBER: 050-BST-PLN-001	PAGE: 18 of 31
TITLE: Statistical Analysis Plan		EFFECTIVE DATE: 14/Nov/2018 REVISION NUMBER: 2.0

[figure not shown]
Study Procedure	Screening Day 1	Screeni ng Day 2	Clinic Admissi on	Baseline (Treatme nt)	Visit Schedule (Days 1 to 28)			8)	Follow- up Schedu le for the highest dose cohorts (Days 29 - 168)		
Study Day a	Day a -(- 28) throug h Day (-7)	Day a -(- 14) through Day (-2)	Day (-1)	Day a 0	Da y 1	Da y 3	Da y 7	Day 14	Da y 21	Da y 28	Day 56, 84, 112, 140, 168
morning(8- 12hr overnight fast) and evening											not visiting the site
Urine Drug Screen	X		X								
Infra-Red thermal imaging of the injected site	X		X		X		X	X	X	X	On Day

Medi Stat Statistics in Medicine	DOCUMENT NUMBER: 050-BST-PLN-001	PAGE: 19 of 31
TITLE: Statistical Analysis Plan		EFFECTIVE DATE: 14/Nov/2018 REVISION NUMBER: 2.0

Study Procedure	Screening Day 1	Screeni ng Day 2	Clinic Admissi on	Baseline (Treatme nt)	Vi	isit Scl	nedule	(Days	s 1 to 2	8)	Follow- up Schedu le for the highest dose cohorts 1 (Days 29 - 168)
Study Day a	Day a -(- 28) throug h Day (-7)	Day a -(- 14) through Day (-2)	Day (-1)	Day a 0	Da y 1	Da y 3	Da y 7	Day 14	Da y 21	Da y 28	Day 56, 84, 112, 140, 168
Infra-Red thermal imaging of the injected site - for 3 rd and 4 th cohort or in cohort 2 if 2 subjects experience intolerable side effects will in cohort 3) k											Every 28 days
Serum Chemistry, Hematology c	X		X		X	X	X	X		X	
Histamine levels d			X		X	X		X			
Urinalysis  Pharmacokinet ics f	X			Pre e X post e	X			X		X	

Medi Stat Statistics in Medicine	DOCUMENT NUMBER: 050-BST-PLN-001	PAGE: 20 of 31
TITLE: Statistical Analysis Plan		EFFECTIVE DATE: 14/Nov/2018 REVISION NUMBER: 2.0

Study Procedure	Screening Day 1	Screeni ng Day 2	Clinic Admissi on	Baseline (Treatme nt)	Visit Schedule (Days 1 to 28)			(8)	Follow- up Schedu le for the highest dose cohorts  1 (Days 29 - 168)		
Study Day a	Day a -(- 28) throug h Day (-7)	Day a -(- 14) through Day (-2)	Day (-1)	Day a 0	Da y 1	Da y 3	Da y 7	Day 14	Da y 21	Da y 28	Day 56, 84, 112, 140, 168
Draize score at the injected site g	X			Pre e X post e	X		X	X	X	X	Every 28 days
Vital signs h	X			Pre e X post e	X		X	X	X	X	
Injection of RZL-012				X							
ECG i	X			X post e	X			X		X	
Pulse rate j				Pre e X post e	X						
Adverse event assessment					X				→		Every 28 days
Adverse event assessment by phone for cohorts 1 and 2											On Day 84 and 112

Study Procedure	Screening Day 1	Screeni ng Day 2	Clinic Admissi on	Baseline (Treatme nt)	Visit Schedule (Days 1 to 28)			28)	Follow- up Schedu le for the highest dose cohorts (Days 29 - 168)		
Study Day a	Day a -(- 28) throug h Day (-7)	Day a -(- 14) through Day (-2)	Day (-1)	Day a 0	Da y 1	Da y 3	Da y 7	Day 14	Da y 21	Da y 28	Day 56, 84, 112, 140, 168
Subjects diary recording weight							X	X	X		On weeks when not visiting the site
Biopsy – In subject of cohort 3 (or in cohort 2 if 2 subjects experience intolerable side effects in cohort 3) k,l											On Day 56

[figure not shown]
- a. Study day is based on Day 0 defined as the day of RZL-012 injection.
- b. Inflammatory markers and cytokines from the 2nd, 3rd and 4th cohorts (on 6 RZL-012 treated and 2 placebo treated subjects in each cohort): CRP, Adiponectin, CD-163, Interleukin [IL]-1β, IL-4, IL-6, IL-10, IL12p70, IL-13, IL-23, Tumor necrosis factor [TNF] α and TGFβ1.
- CBC, coagulation, serum chemistry analysis, renal and liver function, urinalysis, CPK, amylase measurement: before injection, 14d and 28d following injection
- d. Histamine blood level measurement: clinical admission, following drug injection (24h ± 2h), 3d and 14d following injection
- e. Pre/post refers to before/after injection respectively
- f. Pharmacokinetics at the given time points: 0, 30, 60 min, 2h, 3h, 4h, 6h, 8h, 12h, 16h, 24h, 30h in subjects from the 1st, 2nd and 3rd cohorts. Pharmacokinetics will not be conducted in the fourth cohort as the injected dose is divided in 2 clusters 2 weeks apart.

Medi Stat Statistics in Medicine	DOCUMENT NUMBER: 050-BST-PLN-001	PAGE: 22 of 31
TITLE: Statistical Analysis Plan		EFFECTIVE DATE: 14/Nov/2018 REVISION NUMBER: 2.0

- g. Draize score evaluation: before injection, 2h, 24h and 7d,14d,21d and 28d following injection
- h. Vital signs measurement: before injection, 2h, 24h and 7d,14d,21d and 28d following injection
- i. ECG is to be performed in triplicate for all measurements in given time point: 4h, 12h, 24h, Day 14 and 28 following injection
- j. Pulse rate measurements at given time points: 1h, 2h, 4h, 8h, 12h, 24h following injection in the opposite hand of blood sampling
- k. For 3 subjects of cohort 3 (in cohort 2 if 2 subjects experience intolerable side effects in cohort 3) if thermogenesis is evident by thermal camera by Day 56, biopsy from the injected for histology and BAT characterization.
- 1. For subjects from the 3rd (or in cohort 2 if 2 subjects will experience intolerable side effects within the 3rd cohort) and 4th cohort

Medi Stat Statistics in Medicine	DOCUMENT NUMBER: 050-BST-PLN-001	PAGE: 23 of 31
TITLE: Statistical Analysis Plan		EFFECTIVE DATE: 14/Nov/2018 REVISION NUMBER: 2.0

- 5.4.5 Randomization, Blinding and Un-blinding
- 5.4.6 Subjects will be randomized to each study group, i.e., investigational therapy or control, left side injection or right side injection according to a predefined randomization scheme. The investigational therapy group will be treated with RZL-012 and the control group will be treated with the same formulation (vehicle) as with RZL-012, absent active medication
- 5.4.7 Masking will be used to blind the Investigator regarding randomization, i.e., assignment to study group will be disclosed only after subject eligibility is confirmed and immediately before treatment initiation. The pharmacist will be unmasked and will be responsible to fill the syringes for injection.
- 5.5 Selection of study population
  - 5.5.1 Study Population
  - 5.5.2 Male subjects
  - 5.5.3 Age 20 60 years old
  - 5.5.4 The study population include subjects who are obese by Body Mass Index (BMI) definition (27.5 < BMI ≤ 34.9)
  - 5.5.5 Rationale Sample Size Calculation
  - 5.5.6 The planned sample size is 32 subjects (8 in each cohort). 6 subjects per dose group paradigm with the addition of a 2 subjects per control group for all doses. A maximum of 32 evaluable subjects will be included in the study (24 in the RZL-012 treatment arm and 8 in the placebo arm) and followed for as long as 3 months in the 2 lowest dose cohorts, and in the 2 highest dose cohorts for up to 5 months.
- 5.6 Statistical Analysis Software and Data Management
  - 5.6.1 Data manipulation, tabulation of descriptive statistics, calculation of inferential statistics, and graphical representations will be performed using SAS® version 9.3 or higher for Windows. If the use of other software is warranted, the final statistical methodology report will detail what software was used for what purposes.
  - 5.6.2 Data Management
  - 5.6.3 Data management for the study is performed by Spaulding Clinical.
  - 5.6.4 Medical Coding

- 5.6.5 Concomitant medications entered into the database are coded using the WHO (World Health Organization) Drug Public Website Dictionary named WHOCC-ATC/DDD index, which employs the Anatomical Therapeutic Chemical classification system.
- 5.6.6 Adverse events are coded using the most updated version of Medical Dictionary for Regulatory Activities (MedDRA) terminology.
- 5.6.7 Medical history events are coded using the most updated version of Medical Dictionary for Regulatory Activities (MedDRA) terminology
- 5.6.8 Handling of Missing data
- 5.6.9 No imputation of missing data will be performed
- 5.6.10 Protocol Violations and Deviations
- 5.6.11 Departures from the protocol should be avoided unless required for the safety of the subject. Protocol deviations and, if possible, the reason for occurrence will be documented by the study monitor and included in the final clinical study report.
- 5.6.12 The Investigator must report any protocol deviation to the Sponsor and, if required, to the IRB/IEC in accordance with local regulations, within reasonable time. All violations and deviations must be recorded in the study site's electronic system and signed by the Investigator (or designee).

#### 5.7 Subject Population for analyses

[figure not shown]
- 5.7.1 The safety analysis set (SA) will consist of all enrolled subjects who received the study treatment, either RZL-012 or placebo (exposed population), including subjects prematurely withdrawn. All enrolled subjects receiving at least one study drug injection are considered evaluable for the SA set.
- 5.7.2 The SA analysis set will serve as the principal data analysis set for the analyses of the safety endpoints.
- 5.7.3 The efficacy analysis set (EF) will consist of all subjects from the SA analysis set without any major protocol violations measured at baseline
- 5.7.4 The EF analysis set will serve as the principal data analysis set for the analyses of the efficacy endpoints.

Medi Stat Statistics in Medicine	DOCUMENT NUMBER: 050-BST-PLN-001	PAGE: 25 of 31
TITLE: Statistical Analysis Plan		EFFECTIVE DATE: 14/Nov/2018 REVISION NUMBER: 2.0

[figure not shown]
- 5.7.5 The PK analysis set will consist of all subjects with no major deviations related to study drug administration (e.g., incomplete injection of study drug).
- 5.7.6 The PK analysis set will serve as the principal data analysis set for the PK analysis

## 5.8 Statistical Analysis

- 5.8.1 General
- 5.8.2 All measured variables and derived parameters will be listed individually and, if appropriate, tabulated by descriptive statistics. For categorical variables summary tables will be provided giving sample size, absolute and relative frequency. For continuous variables summary tables will be provided giving sample size, arithmetic mean, standard deviation, standard error, coefficient of variation (CV%), median, minimum and maximum of variables, and 95% confidence intervals of means.
- 5.8.3 The data is analyzed using the SAS ® version 9.3 or higher (SAS Institute, Cary North Carolina). Analyses presented in the clinical report but not mentioned in the SAP are unplanned or ad-hoc analyses.
- 5.8.4 Statistical methods presented in the SAP may be slightly different from those that are presented in the protocol. Differences are clearly stated and the SAP supersedes the protocol only with regard to the way data will be handled and analysed.
- 5.8.5 Derived Data
- 5.8.6 Definition of baseline
- 5.8.7 Baseline is defined as the last non-missing value prior to the patient start of treatment (screening or baseline visit).
- 5.8.8 End of Study
- 5.8.9 The end-of-study visit is defined as Day 168.
- 5.8.10 Disposition of subjects (Table 14.1-1 14.1.2)
- 5.8.11 The number of subjects that are randomized into the study, the number of subjects in the Safety, efficacy analysis set, and PK populations, and the number of study completers will be presented.
- 5.8.12 The reasons for early termination/ withdrawal will be summarized.

- 5.8.13 Demographic and Baseline data (Tables 14.1-3-14.1-4)
- 5.8.14 Baseline and demographic data will be summarized in appropriate tables using the Safety population. The data includes demographic characteristics (age and gender) and medical history.
- 5.8.15 Efficacy Analysis
- 5.8.1 The primary endpoint for efficacy is a significant thermogenesis at the injected site compared with the contra-lateral, non-injected site.
- 5.8.2 The average temperature will be presented in a tabular form by visit, side (treated / not treated) and treatment received (RZL-012 / placebo) by cohort and overall. Difference between the sides (treated not treated) will be presented in a tabular form by visit treatment along with the change from baseline (net-delta) in these differences by cohort and overall.
- 5.8.3 Kruskal-Wallis will be used to compare the net-delta between the study arms for the relevant cohorts and visits.
- 5.8.4 The number and percent of subjects with a thermogenic effect, defined as a net-delta ≥ 1, will be presented by cohort and visit for the subjects in the active arm. The duration of the thermogenic effect after the Day 28 visit, for subjects in the active arm with thermogenic effect at the Day 28 visit will be presented.
- 5.8.5 Subcutaneous Fat Mass (SFM) ratio (treated sites / control sites) averaged over the MRI slices will be presented in tabular form by visit, treatment and cohort. The change from baseline in this ratio (in % from the ratio at baseline) will be presented in the same manner, and compared between the treatment arms with Kruskal-Wallis test.
- 5.8.6 Changes from baseline in fasting blood glucose, lipid profile, anthropometric changes, inflammatory markers and cytokines will be presented by visit, treatment, and cohort.
- 5.8.7 Histology results will be presented in tabular form by treatment for relevant subjects.
- 5.8.8 Safety analysis
- 5.8.9 Safety data will be summarized for the Safety population.
- 5.8.10 Adverse events will be coded according to coding dictionaries (the most updated version of MedDRA) and presented in tables by System Organ Class (SOC) and Preferred Term (PT) and by treatment group.

- 5.8.11 The incidence of AEs, as well as the intensity and relationship to study drug will be summarized by treatment group.
- 5.8.12 The incidence of all adverse events will be presented by treatment overall and by cohort along with two sided 95% exact binomial Confidence Interval (CI).
- 5.8.13 The incidence of intolerable side effects will be presented by treatment overall and by cohort along with two sided 95% exact binomial Confidence Interval (CI).
- 5.8.14 Concomitant medication verbatim terms (as recorded on the CRFs) will be coded to Anatomical Therapeutic Chemical (ATC) Level 2 and 4 using the World Health Organization (WHO) dictionary.
- 5.8.15 Interim Analysis
- 5.8.16 An interim analysis is planned at the end of each cohort for evaluation of efficacy. For this purpose, a data lock (except for externally collected data such as PK) will be implemented after each cohort is completed. Upon lack of trends in efficacy due to effect size, the Sponsor will consider study termination

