### 6.1.17.1.2. Efficacy Endpoint – Significant Thermogenesis

The study primary efficacy endpoint, a significant thermogenesis at the injected site will be evaluated by comparing with the contra-lateral, non-injected site. A significant thermogenic effect is defined as the increase of 1 °C from baseline in the difference in temperature (in °C) between the treated and not-treated sites (net delta). This thermogenesis should be apparent by 28 days after injection. The sites temperatures will be measured with a sensitive ( $\pm$  0.1 °C) Infra-Red thermal camera.

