#### 10.5. STATISTICAL ANALYSIS

#### 10.5.1. General

Statistical analysis will be performed using SAS V9.4 or higher (SAS Institute, Cary NC, USA).

Statistical analyses will be mainly descriptive in nature where study data will be tabulated and summarized using the mean, standard deviation or standard error, median, minimum, maximum and number of subjects by cohort for continuous data. For categorical data, results will be summarized via a count and percentage by cohort. The effects of noncompliance, dropouts, and covariates, may be assessed to determine the impact on the general applicability of results from this study.

If any statistical tests are performed, they will be two-sided. The required significance level of findings will be equal to or lower than 5%. Nominal p-values will be presented.

Where confidence limits are appropriate, the confidence level will be 95%.

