#### 10.5.5. Efficacy Analysis

The average temperature will be presented in a tabular form by visit, site (treated / not treated) and treatment received (RZL-012 / placebo) by cohort and overall. Difference between the sites (treated – not treated) will be presented in a tabular form by visit treatment along with the change from baseline (net-delta) in these differences by cohort and overall.

Non-parametric tests will be used to compare the net-delta between the study arms for the relevant cohorts and visits.

The number and percent of subjects with a thermogenic effect, defined as a net-delta  $\geq 1$ , will be presented by cohort and visit for the subjects in the active arm. The duration of the thermogenic effect after the Day 28 visit, for subjects in the active arm with thermogenic effect at the Day 28 visit will be presented.

Subcutaneous Fat Mass (SFM) ratio (treated sites / control sites) averaged over the MRI slices will be presented in tabular form by visit, treatment and cohort. The change from baseline in this ratio (in % from the ratio at baseline) will be presented in the same manner, and compared between the treatment arms with non-parametric tests.

Changes from baseline in fasting blood glucose, lipid profile, anthropometric changes, inflammatory markers and cytokines will be presented by visit, treatment, and cohort.

Histology results will be presented in tabular form by treatment.

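### The SAP does not say whether its arm comparison is pooled or per cohort; a pooled Day 28 comparison would gain precision from adjusting for baseline and cohort

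*SAP*

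**What the plan says.** Numbering inside SAP 5.8 restarts under Efficacy Analysis. The item numbers below are the ones under that heading unless marked otherwise.

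- **Outcome.** Net-delta is the change from baseline in the temperature difference between the treated and the untreated side (Protocol 6.1.17.1.2). SAP 5.8.2 tabulates the side differences "along with the change from baseline (net-delta) in these differences by cohort and overall".
- **Temperature test.** SAP 5.8.3: "Kruskal-Wallis will be used to compare the net-delta between the study arms for the relevant cohorts and visits". Protocol 10.5.5 is less specific: "Non-parametric tests will be used to compare the net-delta between the study arms for the relevant cohorts and visits".
- **MRI.** For the subcutaneous fat mass (SFM) ratio, SAP 5.8.5 states: "The change from baseline in this ratio (in % from the ratio at baseline) will be presented in the same manner". That percentage change is then "compared between the treatment arms with Kruskal-Wallis test".
- **Covariates.** The only mention is in Protocol 10.5.1: "The effects of noncompliance, dropouts, and covariates, may be assessed". No covariate or model is named there or in the SAP.
- **Allocation.** Each of the four cohorts has 6 active and 2 placebo subjects. Within each, "the first 3 subjects will be forced randomized into 2 active and 1 control" (SAP 5.4.3), which by subtraction leaves 4 active and 1 placebo among the last five. Neither document calls these blocks strata. The randomisation plan is a separate document (SAP 6.2).

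**The concern.** Subtracting baseline fixes its slope at 1. If follow-up is only partly correlated with baseline, that over-corrects. Measurement noise in the baseline enters the change score in full, and a chance difference between arms at baseline pushes the estimated effect the other way. With 8 placebo subjects in all, such imbalance can be sizeable. The data needed to reduce it are already collected: thermal images of both sides at screening and Day -1, and MRI at the second screening visit (Protocol 6.1.12 and 6.1.13).

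Thermogenesis is the primary efficacy endpoint, p-values for the group difference are planned (SAP Table 14.2.1-2), and the sponsor may consider stopping for lack of an efficacy trend (SAP 5.8.16). The precision of the arm difference therefore matters. SAP 5.8.3 under General also classes any analysis not mentioned in the SAP as unplanned or ad hoc, so an adjusted comparison added later would carry that label.

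**Working it through.** **Inputs from the documents.** 4 × (6 + 2) = 32 subjects, 24 active and 8 placebo, which reproduces the stated sample size (SAP 5.5.6). No power, effect size, SD or baseline to follow-up correlation is given.

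**Assumed.** A correlation r between baseline and Day 28 side difference of 0.2 to 0.8, and equal variance s² at both times.

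**Step 1: large-sample formula.**

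- Change score: variance 2(1 − r)s².
- Baseline-adjusted (ANCOVA): variance (1 − r²)s².
- Ratio: (1 + r)/2, which is 0.60, 0.75, 0.80 and 0.90 at r = 0.2, 0.5, 0.6 and 0.8.

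**Step 2: small-sample correction.** Estimating the baseline slope multiplies the adjusted variance by 1 + 1/(f − 2), where f is the residual degrees of freedom before the covariate is added.

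- Pooled with cohort terms: f = 32 − 4 − 1 = 27, factor 1 + 1/25 = 1.04.
- One cohort: f = 8 − 2 = 6, factor 1 + 1/4 = 1.25.

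| Assumed r | Pooled 24 v 8: ratio | Variance change | One cohort 6 v 2: ratio | Variance change |
|---|---|---|---|---|
| 0.2 | 0.60 × 1.04 = 0.624 | −37.6% | 0.60 × 1.25 = 0.750 | −25% |
| 0.5 | 0.75 × 1.04 = 0.780 | −22.0% | 0.75 × 1.25 = 0.9375 | −6.25% |
| 0.6 | 0.80 × 1.04 = 0.832 | −16.8% | 0.80 × 1.25 = 1.000 | 0 |
| 0.8 | 0.90 × 1.04 = 0.936 | −6.4% | 0.90 × 1.25 = 1.125 | +12.5% |

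Simulation (20,000 runs per scenario) gave reductions of 38.5%, 21.6%, 16.7% and 6.1% pooled. In one cohort it gave reductions of 24.9%, 5.8% and 0, then an increase of 14.2%.

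A single cohort also loses a degree of freedom: the t critical value rises from 2.447 to 2.571, and (2.571/2.447)² = 1.104. On interval width, adjustment then helps only if r is below 2/(1.25 × 1.104) − 1, or about 0.45.

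**Step 3: chance imbalance.** The difference in mean baseline between arms has SD √(1/24 + 1/8) = 0.41 between-subject SD. A change score shifts the arm difference by −(1 − r) times the imbalance. At r = 0.5, an imbalance of one SD gives 0.5 × 0.41 ≈ 0.2 SD.

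**Step 4: the rank test actually planned.** The formula concerns mean differences, so it was checked against Kruskal-Wallis by simulation. The setting was 24 v 8, normal data, an assumed effect of 1 SD in every cohort and no cohort effect. The comparator was ANCOVA with baseline and cohort and a permutation p-value.

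| Assumed r | Pooled Kruskal-Wallis on change: power | Permutation ANCOVA: power |
|---|---|---|
| 0.2 | 40% | 64% |
| 0.5 | 62% | 74% |
| 0.8 | 94% | 96% |

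Type I error was 4–6% for both. Repeat runs moved the powers by a few percentage points.

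**Step 5: why pooled or per cohort must be stated.** For 6 v 2 there are C(8,2) = 28 allocations. The largest Kruskal-Wallis statistic is 4.0, with exact p = 2/28 = 0.071 and chi-square p = 0.0455. With exact p-values, no single-cohort test can reach 5%.

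**The case against.** The case against is substantial.

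- **The plan is exploratory.** Protocol 10.5.1 calls the analyses mainly descriptive with nominal p-values, and no power is claimed. Arm and injection side are both randomised and net-delta is already controlled by the other side of the abdomen. A reader might infer that the change-score comparison is biased. It is not: averaged over randomisation it is unbiased, and the shift in step 3 is conditional on a given imbalance. This stands, and it limits the point to efficiency.
- **The size is assumed.** A reader might take the large-sample range of 10–40%, which is (1 − r)/2, as a property of this trial. The documents cannot support that. The range comes wholly from the chosen r, and the corrected pooled range is about 6–38%.
- **Adjustment can hurt.** Per-cohort testing is a natural reading of SAP 5.8.3, and there adjustment may lose precision. This stands; the recommendation is for the pooled comparison only.
- **The SFM ratio is not a raw change score.** It is analysed as a percentage change, so the figures above do not carry over to it. This stands.
- **The strata are not established.** A reader might infer that the SAP ignores named randomisation strata, but none are named. A within-cohort test already conditions on cohort. The three/five split may also not survive replacements in cohorts 3 and 4 (Protocol 5.4) or exclusions from the efficacy set (SAP 5.7.3).
- **Pooling averages over doses.** Protocol 10.1 seeks the tolerated dose with the largest thermogenic effect, and in the earlier trial the temperature rise was mostly at the highest dose (Protocol 1.2.4). A pooled contrast does not rank doses, and it is diluted if the low doses do little.

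None of this removes the core observation: the baseline is collected but not used as a covariate, no cohort term is planned, and the unit of testing is unstated.

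**Conclusion.** The point holds as a minor efficiency improvement, not an error in validity. Both between-arm tests omit baseline and cohort, and the SAP leaves open whether they are pooled.

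For a pooled Day 28 comparison of the temperature side difference, adjustment would reduce the variance of the arm difference by about 38% at r = 0.2, 22% at r = 0.5 and 6% at r = 0.8. This rests on an assumed r, equal variances at the two times and all 32 subjects being analysed. It is indicative only for a rank test, although the simulated gain over pooled Kruskal-Wallis points the same way under its assumed 1 SD effect. In a single 6 v 2 cohort there is no gain from about r = 0.6 (about 0.45 on interval width), so adjustment should not be used there.

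**What to change.** 1. State in SAP 5.8.3 and 5.8.5 that the all-cohort RZL-012 v placebo comparison is pooled and stratified by cohort.
2. Add a Day 28 ANCOVA of the temperature side difference, and of the log SFM ratio, with the baseline value as covariate and cohort as factor. Report the estimate with its confidence interval.
3. Take the p-value by permuting treatment labels within cohort. Permute within the first-three and last-five blocks as well if the randomisation plan confirms them and they remain intact in the analysed set. That would give C(3,1) × C(5,1) = 15 allocations per cohort and 15⁴ = 50,625 in all.
4. Keep net-delta for the by-cohort tables and the 1 °C responder count, and do not apply the adjustment within single cohorts.

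The cost is SAP wording and a short program, with no extra subjects or visits. There are two downsides: the estimate assumes a linear relation with baseline (the permutation p-value does not depend on it), and the pooled contrast averages over doses.
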